Product Name	Relivion™ (Device version RLV3; SW version 0.3.21 ; App Version 1.0)
Sponsor	Neurolief Ltd.
US Agent	[name]. SciVance Consulting [name]
Indication under investigation	The Relivion™ is a non-invasive transcutaneous neuro-stimulator intended for treatment of headache and is indicated for the acute treatment of migraine with or without aura in subjects 18 years of age or older. The Relivion is intended to be a prescription device, self-used at home.
Investigation Purpose	The RIME Study will evaluate the safety and efficacy of a self-administered abortive treatment for migraine headache using combined occipital and supraorbital transcutaneous nerve stimulator (Relivion™). This pivotal clinical investigation is intended to support the clinical evaluation of Neurolief's Relivion device in the context of its initial FDA clearance under 21 CFR part 882.5891, Transcutaneous electrical nerve stimulator to treat headache.
Product Status	Pre-market
Patient Population	Male and Female subjects, 18 years of age and older suffering from migraine headache with and without aura.
Primary Objectives	To assess the headache pain relief from baseline to 2 hours post-treatment, without rescue medications, when using active combined occipital and supraorbital transcutaneous nerve stimulation (Relivion™) compared to sham stimulation, in subjects suffering from acute migraine headache. Pain score will be assessed on a 4-point scale whereas 0 =no pain, 1=Mild pain, 2=Moderate pain, 3= Severe pain

Secondary Objectives	
 1. To assess the proportion of subjects reporting improvement in their most bothersome migraine-associated symptom (MBS) other than a headache, without rescue medications, 2 hours from Relivion™ treatment initiation compared to sham stimulation, in subjects suffering from acute migraine headache. MBS may be nausea, photophobia or phonophobia. 2. To assess the proportion of subjects reporting headache relief at 1-hour without rescue medications, compared to sham stimulation. 3. To assess the proportion of subjects who are pain free at 2 hours from Relivion™ treatment initiation without rescue medications, compared to sham stimulation, in subjects suffering from acute migraine headache.
Safety Objective	To demonstrate safety in using the Relivion™ device.
Exploratory Objectives	
 1. To assess the proportion of subjects reporting freedom from their MBS other than a headache, without rescue medications, 2 hours from Relivion™ treatment initiation compared to sham stimulation, in subjects suffering from acute migraine headache. 2. To assess the proportion of subjects who are pain free at 1-hour post Relivion™ treatment initiation (if rescue therapy was not used), in their first treated migraine attack. 3. To assess the subjects positive Global Impression of Effect of study device at the end of the study, defined as satisfied or very satisfied using a simple Likert-type scale whereas 1 = Very dissatisfied, 2 = dissatisfied, 3 = unsure, 4 = satisfied, 5 = Very satisfied, in active versus sham stimulation. 4. To assess the proportion of subjects reporting headache relief without taking rescue medications within 2 and 24 hours from Relivion™ treatment initiation compared to sham stimulation, in subjects suffering from acute migraine headache.
Planned Study Duration	Each subject will participate in the study for up to 110 days (~16 weeks) including the run-in period. The overall enrollment period is expected to last approximately 12 months.
Study Design	
Multi-center, prospective, 2-arms randomized, double-blind, parallel-group, sham controlled study. The study will include the following study periods:
 
 • Run-in Period (28+10 days) • Randomization to Relivion™ vs. Sham control (1:1 randomization) and Self-Practice Period (up to 14 days) • Treatment Period (up to 5 migraine attacks or 70±10 days from randomization visit, whichever comes first) 
After completion of the Treatment Period the subject's participation will be over.

	
The study will be conducted at a maximum of 12 investigational sites in the United States (US) and Israel; Sites in the US will enroll approximately 33% of total subjects. Each site will enroll a maximum of 60 subjects.

Randomization	
Upon completion of the run-in period, eligible subjects will be randomly allocated (with a 1:1 ratio) to one of the following 2 treatment groups based on a randomization scheme using the permuted block method stratified by center:
 
 • Group A - active stimulation • Group B - sham stimulation 
The randomization scheme will be prepared by the study statistician using the SAS (version 9.4.) random number procedure. The block size will be random, and all study personnel will be therefore blinded to the randomization block size.

Sample Size	
The planned sample size is up to 200 randomized subjects, to allow for 90 evaluable subjects per treatment group, anticipating 10% drop-out.
 
One interim analysis is planned after 144 (80%) evaluable subjects have been accrued.

Inclusion Criteria	
 1. Subjects 18 years of age and older. 2. Subject meets the ICHD-3 (2018) diagnostic criteria for Migraine with or without aura. 3. Subject reports 1-6 Migraine attacks per month; other headaches no more than 6 days per month. 4. Subject is willing to and capable of complying with the specified study requirements, provided written Informed Consent, can complete the electronic diaries, and can be contacted by telephone.
Exclusion Criteria	
 1. Subject having received Botox treatment in the head region in the prior 3 months. 2. Subject having received supraorbital or occipital nerve blocks in the prior month. 3. Past 6 months of chronic migraine, New Daily Persistent Headache, and chronic tension-type headache per ICHD-3 (2018) diagnostic criteria. 4. Current medication overuse headache. 5. Use of opioid medications in the prior 1 month. 6. Use of barbiturates in the prior 1 month.

	
 7. Subject has >10 headache days per month 8. Implanted metal/shrapnel or electrical devices in the head (not including dental implants), a cardiac pacemaker or an implanted or wearable defibrillator. 9. Received parenteral infusions for migraine within the previous 2 weeks. 10. Subject has known uncontrolled epilepsy. 11. History of neurosurgical interventions 12. Subject with implanted neurostimulators, surgical clips (above the shoulder line) or any medical pumps. 13. Current drug abuse or alcoholism. 14. Subject is participating in any other clinical study. 15. Skin lesion or inflammation at the region of the stimulating electrodes. 16. Personality or somatoform disorder. 17. Pregnancy or Lactation. 18. Women with child bearing potential without medically acceptable method of contraception (NOTE: Females of child bearing potential must have a negative pregnancy test). 19. Documented history of cerebrovascular event. 20. Subject with recent brain or facial trauma (occurred less than 3 months prior to this study). 21. Subject participated in a previous study with the Relivion device. 22. The subject does not have the basic cognitive and motor skills needed to operate a smartphone. 23. Subject with head circumference smaller than 51 centimeters or head circumference larger than 60 centimeters 24. Subject with other significant pain problem that in the opinion of the investigator may confound the study assessments.
Primary Efficacy Endpoint	
Proportion of subjects reporting reduction of migraine headache pain 2 hours post treatment initiation from severe or moderate to mild or no pain, or from mild to no pain, in their first eligible (per section 9.1.6) treated migraine attack, when using active combined occipital and supraorbital transcutaneous nerve stimulation compared to sham stimulation, in subjects suffering from acute migraine headache. Use of rescue medication prior to 2 hours post treatment initiation will be considered a failure for this end-point (i.e. patient will be assigned the status of no reduction).

Secondary Efficacy Endpoints	
 1. Proportion of subjects reporting improvement in their MBS other than a headache, 2 hours post-treatment initiation (if rescue therapy was not used), in their first eligible treated migraine attack. MBS may be nausea, photophobia, phonophobia as defined by each subject prior to beginning of the treatment. 2. Proportion of subjects reporting reduction of migraine headache pain 1-hour post treatment initiation (if rescue therapy was not used), from severe or moderate to mild or no pain, or from mild to no pain, in their first eligible treated migraine attack. 3. Proportion of subjects who are pain free at 2 hours post treatment initiation (if rescue therapy was not used), in their first eligible treated migraine attack.
Safety Endpoint	Safety of the study device following study treatment: Rate of Adverse events related or unrelated to the study device [Time Frame: 24 hours post treatment initiation].
Exploratory Endpoints	
 1. Proportion of subjects reporting freedom from their MBS other than a headache, 2 hours post-treatment initiation (if rescue therapy was not used), in their first eligible treated migraine attack. 2. Proportion of subjects who are pain free at 1-hour post treatment initiation (if rescue therapy was not used), in their first eligible treated migraine attack. 3. Proportion of subjects rating the subjects positive (score of 4 or 5) Global Impression of Effect of study device at the end of the study, defined as satisfied or very satisfied using a simple Likert-type scale whereas 1 = Very dissatisfied, 2 = dissatisfied, 3 = unsure, 4 = satisfied, 5 = Very satisfied. 4. Proportion of subjects reporting 2-24h headache relief, defined as headache relief at 2 hours without rescue medications, then no moderate to severe headache in the next 22 hours, and no use of rescue medication or additional stimulation, in their first eligible treated migraine attack.
Statistical Considerations	
Study Hypothesis:
 $H_0: P_T = P_S$ $H_A: P_T \neq P_S$ 
Where P_T and P_S represent the proportion (%) of subjects reporting pain relief in the active treatment group and sham group respectively
 
Sample Size Estimation:
 
The sample size for this study was calculated to test the null hypothesis with a chi-squared test, even though the final analysis may employ a regression model and/or a Fisher's exact test.
 
Sample sizes are calculated to test the null hypothesis with 80% power at a 5% level of significance.

If we assume that 45% of the subjects in the active treatment arm will have successful pain relief versus 25% in the sham arm, 180 evaluable subjects are required, 90 per group. Allowing for a ~10% drop-out rate, a total of 200 (100 active vs. 100 sham) subjects should be enrolled in the study.

Interim Analysis:

One interim analysis is planned after 144 (80%) evaluable subjects have been accrued. The study will then either continue to the originally planned sample size if the result is “favorable”, stop for futility if the result is “unfavorable”, or an increase will be made to the sample size if the result is “promising” these decisions will be made based on the conditional power (CP), defined as the conditional probability that the final result will exceed a critical value at the interim given the observed effect size $\widehat{\delta}_1$ = difference between pain reduction rates in the active versus control groups at the interim look.

Primary endpoint analysis:

The primary endpoint is the proportion of subjects reporting reduction of migraine headache pain 2 hours post treatment initiation from severe or moderate to mild or no pain, or from mild to no pain, in their first treated migraine attack, when using active combined occipital and supraorbital transcutaneous nerve stimulation compared to sham stimulation, in subjects suffering from acute migraine headache. Use of rescue medication will be considered a failure for this end-point (i.e. patient will be assigned the status of no reduction).

A count and percentage of subjects reporting such headache pain reduction without rescue medications will be calculated and presented for both study groups, each with a two-sided 95% exact confidence interval. The groups will be compared with a chi-squared test and a Fisher’s exact test.

If the null hypothesis is rejected in favor of the alternative hypothesis and the proportion (%) of subjects reporting reduction of migraine in the treated group is greater than that of the sham group, the study will be deemed successful.

3. Introduction

3.1. Background

Migraine is a prevalent and debilitating primary headache disorder. In the U.S population the prevalence of migraine is approximately 18% in women and 6% in men [1]. The World Health Organization (WHO) estimates that half to three quarters of adults aged 18-65 years in the world have had headache in the last year and, among those individuals, 30% or more have reported migraine [2]. Migraine prevalence is highest in those aged 30 to 39 years [3]. Migraine patients suffer from disabling symptoms that usually consist of a moderate to severe headache lasting 4 to 72 hours, nausea and/or vomiting, phonophobia (noise sensitivity) and photophobia (light sensitivity). Seventy five percent (75%) have a reduced ability to function during the migraine episodes and 33% require bed rest during their attacks [3]. Patients with migraine are often refractory to medical treatment and some of the most effective anti-migraine drugs, such as Triptans, have substantial side effects [4].

Triptans are the first-line therapy for patients whose attacks do not reliably respond to simple or combination analgesics [4]. The Most common side effects of Triptans are dizziness, nausea, weakness, tiredness, drowsiness, paresthesias, flushing, neck tightness and chest pressure which occur in about 20% of patients. Triptans have also been associated with the development of headache caused by medication overuse. Therefore, most experts recommend a conservative limit on its use to about 2 days per week [2]. Serious cardiovascular events, some resulting in death, have been reported in association with the use of Triptans. Thus, Triptans are contraindicated in an estimated 4.7 million Americans with migraine [4]. These contraindications and side effects have left millions of patients without a proper solution for their pain. Therefore, these patients may benefit from other, non-pharmaceutical strategies to modulate their pain. One of the tools to achieve pain reduction is Peripheral Nerve Stimulation (PNS). PNS can be applied either invasively or non-invasively. Invasive PNS involves surgery that places a small electrical device next to one of the peripheral nerves. Invasive procedures of PNS for treatment of migraine include occipital nerve stimulation (ONS) which has been shown to provide relief for chronic migraine in numerous clinical trials [5-9]. Another more recent PNS procedure for treatment of migraine combines both occipital and supraorbital nerve stimulation [10,11]. Recent clinical studies support the expectation that applying peripheral nerve stimulation to a combination of the occipital and supraorbital nerves may result in a better outcome compared to stimulation of the occipital nerve alone [10,11]. Indeed, the response rate for patients with intractable head-wide pain who were treated with implanted PNS to the occipital and supraorbital nerve is reported to be better than 90% [10,11]. This is an improvement from using stimulation to the occipital nerves only which is reported to bring about just a 40% response rate [10]. However, implanted peripheral nerve stimulation remains an invasive and costly procedure with high rate of complications including infection, bleeding or fluid collection under the skin, as well as hardware-related malfunctions such as migration and breakage of the implanted leads and pulse generator failure [5]. Thus, these procedures are currently offered only for intractable severe cases of chronic migraine.

Transcutaneous nerve stimulation is a noninvasive technique that for decades was considered of potential benefit for patients with headache [12]. Supraorbital transcutaneous stimulation has been applied and found to be safe and effective as a prophylactic therapy for migraine. In a sham-controlled trial, therapeutic gain was found to be within the range of those reported for other preventive drug and non-drug antimigraine treatments [13]. In a safety and patients' satisfaction survey of 2,313 patients using transcutaneous supraorbital stimulation, no serious adverse events were reported [14]. In a recent trial [15] of supraorbital stimulation for acute treatment of migraine, a significant difference was shown in pain reduction between the sham and active treatment, with no significant adverse events.

Due to the challenge of transferring current through the hair, stimulation of the occipital nerve is mostly performed with implanted [5,6,8,16] and percutaneous [17] nerve stimulators. However, due to its superficial anatomic location at the level of the external occipital protuberance [18, 19] once the electrodes are placed under the hair and close enough to the scalp, it can be stimulated transcutaneously. It may thereby provide similar clinical benefits without the risks associated with an invasive procedure. A combined occipital and supraorbital stimulation by means of transcutaneous nerve stimulation may provide a safe, effective and fast acting treatment for reducing migraine related pain.

According to this rationale, Neurolief is developing the Relivion™ - a transcutaneous neuro-stimulator applying combined occipital and supraorbital transcutaneous nerve stimulation for treatment of migraine. Following completion of early clinical studies showing favorable results, Neurolief designed the proposed clinical trial to evaluate the safety and efficacy of the Relivion™ in a two-arms controlled, double blinded randomized study.

3.2. Purpose

The RIME Study will evaluate the safety and efficacy of a self-administered abortive treatment for migraine headache using combined occipital and supraorbital transcutaneous nerve stimulator (Relivion™).

This pivotal clinical investigation is intended to support the clinical evaluation of Neurolief's Relivion™ device in the context of its initial FDA clearance under 21 CFR part 882.5891, Transcutaneous electrical nerve stimulator to treat headache.

4. Objectives and Endpoints

4.1. Objectives

4.1.1. Primary Objective

To assess the headache pain relief from baseline to 2 hours post-treatment, without rescue medications, when using active combined occipital and supraorbital transcutaneous nerve stimulation (Relivion™) compared to sham stimulation, in subjects suffering from acute migraine headache. Pain score will be assessed on a 4-point scale whereas 0 =no pain, 1=Mild pain, 2=Moderate pain, 3= Severe pain

4.1.2. Secondary Objectives

1. To assess the proportion of subjects reporting improvement in their most bothersome migraine-associated symptom (MBS) other than a headache, without rescue medications, 2 hours from Relivion™ treatment initiation compared to sham stimulation, in subjects suffering from acute migraine headache. MBS may be nausea, photophobia or phonophobia.
2. To assess the proportion of subjects reporting headache relief at 1-hour without rescue medications, compared to sham stimulation.
3. To assess the proportion of subjects who are pain free at 2 hours from Relivion™ treatment initiation without rescue medications, compared to sham stimulation, in subjects suffering from acute migraine headache.

4.1.3. Safety Objective

To demonstrate safety in using the Relivion™ device.

4.1.4. Exploratory Objectives

1. To assess the proportion of subjects reporting freedom from their MBS other than a headache, without rescue medications, 2 hours from Relivion™ treatment initiation compared to sham stimulation, in subjects suffering from acute migraine headache.
2. To assess the proportion of subjects who are pain free at 1-hour post Relivion™ treatment initiation (if rescue therapy was not used), in their first treated migraine attack.
3. To assess the subjects positive Global Impression of Effect of study device at the end of the study, defined as satisfied or very satisfied using a simple Likert-type scale whereas 1 = Very dissatisfied, 2 = dissatisfied, 3 = unsure, 4 = satisfied, 5 = Very satisfied, in active versus sham stimulation.
4. To assess the proportion of subjects reporting headache relief without taking rescue medications within 2 and 24 hours from Relivion™ treatment initiation compared to sham stimulation, in subjects suffering from acute migraine headache.

 Neurolief Brain Innovation	THE RIME STUDY: ABRIDGED CLINICAL INVESTIGATION PLAN	Doc No.: CL-CIP-001 Abridged Ref Rev: REV.2 / 11JUN2019 Pg. 15 of 41
--	---	--

4.2. Endpoints

4.2.1. Primary Efficacy Endpoint

Proportion of subjects reporting reduction of migraine headache pain 2 hours post treatment initiation from severe or moderate to mild or no pain, or from mild to no pain, in their first eligible treated migraine attack, when using active combined occipital and supraorbital transcutaneous nerve stimulation compared to sham stimulation, in subjects suffering from acute migraine headache.

Use of rescue medication will be considered a failure for this end-point (*i.e.* patient will be assigned the status of no reduction).

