 - Subject will initiate the treatment procedure by turning on the device and the dedicated mobile application. The mobile application will guide the subject through the treatment procedure steps and will direct him/her to the study Patient Reported Outcome diary when required.
 - Prior to initiating the treatment, subject will report on the Patient Reported Outcome diary that:
 - He/she did not use analgesics or other pain relief drugs or cannabis within 4 hours period before the treatment.
 - Confirm no more than 30 minutes have passed since Migraine episode headache initiated.
 - Confirm that at least 48 pain free hours have passed since the subject previous Migraine episode.
 - Confirm he/she did not wake up with a Migraine headache.
- In case subject used analgesics or other pain relief drugs or cannabis within 4 hours period before the treatment initiation and/or more than 30 minutes passed from the start of the migraine episode and/or less than 48 pain free hours have passed since subject's previous Migraine episode and/or subject woke up with a Migraine headache, subject will be instructed to refrain from using the device and await his/her next migraine episode.
- Prior to initiation of treatment and no later than 30 minutes from Migraine headache pain initiation, subject will document on the Patient Reported Outcome diary his/her baseline migraine pain level (whereas 1=Mild pain, 2=Moderate pain, 3=Severe pain) and the most bothersome migraine-associated symptom (nausea, photophobia, phonophobia or none).
- Subject will then initiate the treatment along with the dedicated mobile application. The treatment will last 60±30 minutes. The Relivion™ device programmed treatment duration will be 1 hour. In case an earlier substantial pain relief is achieved, subject may stop treatment earlier but not less than 30 minutes from treatment start. If necessary, treatment can be paused by the

 Neurolief Brain Innovation	THE RIME STUDY: ABRIDGED CLINICAL INVESTIGATION PLAN	Doc No.: CL-CIP-001 Abridged Ref Rev: REV.2 / 11JUN2019 Pg. 27 of 41
--	---	--

subject and then be resumed. Treatment with total stimulation time of at least 30 minutes of a "pass" session on the device log timeline, will count as a completed treatment.

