11.3. Sample Size Estimation

The sample size for this study was calculated to test the null hypothesis with a chi-squared test, even though the final analysis may employ a regression model and/or a Fisher's exact test.

The sample size is calculated to test the null hypothesis with 80% power at a 5% level of significance using the POWER procedure in SAS v9.4.

If we assume that 45% of the subjects in the active treatment arm will have successful pain relief versus 25% in the sham arm then 180 evaluable subjects are required, 90 per group. Allowing for a ~10% drop-out rate, a total of 200 (100 active vs. 100 sham) subjects should be enrolled in the study.

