11.7. Statistical Analysis

11.7.1. General Considerations

Statistical analyses will be performed using SAS® v9.4 (SAS Institute, Cary NC, USA). Statistical analyses and reporting will be performed in compliance with FDA Guidance E6 GCP, 21 CFR part 812, E9 and ISO 14155.

All statistical tests will be two-sided. The required significance level of findings will be equal to or lower than 5%, nominal p-values will be presented. Where confidence limits are appropriate, the confidence level will be 95%.

Continuous variables will be summarized by a mean, standard deviation, minimum, median and maximum and categorical variables by a count and percentage. For comparison of means (continuous variables), the two-sample t-test or the Wilcoxon rank sum test will be used as appropriate. For comparison of proportions (categorical variables), the chi-squared test or Fisher's exact test will be used as appropriate.

If multiple measurements are taken in a single patient, statistics described below will be appropriately modified to accommodate the within patient correlation.

Deviations from the planned analysis will be described, with proper justification, in the clinical study report.

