11.7.5. Efficacy Analysis

Primary Efficacy Analyses

The primary endpoint is the proportion (%) of patients reporting reduction in their pain level 2 hours post-treatment without rescue medications from severe or moderate to mild or no pain, or from mild to no pain, in their first treated eligible (per **Section 9.1.6**) migraine attack (excluding the "self-practice" treatment). A count and percentage of subjects reporting such headache pain reduction without rescue medications will be calculated and presented for both study groups, each with a two-sided 95% exact confidence interval. The groups will be compared with a chi-squared test and a Fisher's exact test.

If the null hypothesis is rejected in favor of the alternative hypothesis and the proportion (%) of subjects responding to this endpoint in the active group is greater than that of the sham group, the study will be deemed successful.

The primary endpoint will also be evaluated stratified by center using a Mantel-Haenszel test to assess the center by group interaction.

A sensitivity analysis of the primary end-point will be performed to assess the impact of missing data on the study outcome. This will be performed using several possible imputation methods.

Subset Analyses of Primary Endpoint

Adjustment for other covariates such as demographics or other baseline patient characteristics may be performed by adding these variables into a logistic regression model.

Subgroup analysis will be performed and reported by adding the variables listed below to a logistic regression model:

- use of migraine medications
- blinding assessment
- US vs. OUS sites

Secondary Efficacy Analyses

The secondary efficacy variables will be summarized by a count and percentage and compared with a chi-squared test and a Fisher's exact test.

Exploratory Analyses

The exploratory variables will be summarized by a count and percentage and compared with a chi-squared test and a Fisher's exact test.

Global Impression of Effect will also be summarized by descriptive statistics per treatment group and compared between the groups with a t-test.

Frequency of use of rescue medications will be summarized by descriptive statistics per treatment group and compared between the groups with a t-test.

Safety Analysis

The primary safety variable, the cumulative incidence (and 95% CI) of device related adverse events (AEs) throughout the study, will be presented in tabular format and will include incidence tables by severity.

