5. Proportion of subjects who were free of pain in at least 50% of their eligible treated attacks at each timepoint.
6. Proportion (%) of attacks for which patients reporting reduction in their pain level without rescue medications from severe or moderate to mild or no pain, or from mild to no pain, from all treated eligible migraine attack at each timepoint (excluding the "self-practice" treatment).
7. Proportion of attacks for which subjects reporting improvement in their MBS other than a headache (if rescue therapy was not used), from all eligible treated migraine attack at each timepoint. MBS may be nausea, photophobia, phonophobia as defined by each subject prior to beginning of the treatment.
8. Proportion of attacks for which subjects reporting pain free (if rescue therapy was not used), from all eligible treated migraine attack at each timepoint.
9. Proportion of attacks for which subjects reporting freedom of MBS other than a headache (if rescue therapy was not used), from all eligible treated migraine attack at each timepoint. MBS may be nausea, photophobia, phonophobia as defined by each subject prior to beginning of the treatment.
10. Proportion (%) of patients with pain level moderate/severe at baseline reporting reduction in their pain level 1, 2 and 24 hours post-treatment without rescue medications, to mild or no pain, in their first treated eligible migraine attack (excluding the "self-practice" treatment).
11. Proportion (%) of patients with pain level moderate/severe at baseline reporting pain freedom at 1, 2 and 24 hours post-treatment without rescue medications, in their first treated eligible migraine attack (excluding the "self-practice" treatment).

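### The stated primary test leaves out baseline pain, which sets the response hurdle; stratifying by it would improve a test that is already valid

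*Protocol*

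**What the plan says.** Protocol 4.2.1 and SAP 2.1 define response at 2 hours, without rescue medication, as a reduction "from severe or moderate to mild or no pain, or from mild to no pain" in the first eligible treated attack. A mild attack must become pain free; a moderate or severe attack need only become mild.

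Protocol 8.1.6 has the subject record pain in the diary before starting treatment ("whereas 1=Mild pain, 2=Moderate pain, 3=Severe pain"), within 30 minutes of headache onset. Mild attacks may therefore be treated, and the level is known for each treated attack.

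For the primary comparison, Protocol 11.7.5 states: "The groups will be compared with a chi-squared test" and a Fisher's exact test. The same section adds:
- a Mantel-Haenszel analysis by center;
- subgroup models for migraine medication use, blinding assessment and US versus non-US sites;
- optional logistic adjustment for baseline characteristics, without naming baseline pain.

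Randomization is stratified by center only (Protocol 8.4 and 11.5). SAP 2.3 adds, among further analyses, "Proportion (%) of patients with pain level moderate/severe at baseline reporting reduction in their pain level" (item 10) and the matching pain-freedom analysis (item 11). The SAP Introduction says that enrollment has stopped, that 109 subjects have primary endpoint data, and that those data remain blinded.

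**The concern.** The variable that sets the success criterion plays no committed part in the test of that criterion. If response rates differ between mild and moderate/severe attacks, an unadjusted comparison leaves that variation in the error term. A chance excess of mild attacks in one arm then moves the observed difference. The pain level of the first attack is not known at randomization, so only the analysis can deal with it.

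The matter weighs more at 109 subjects than at the planned 180, because chance imbalances are larger and there is less power to spare. Because adjustment is optional and no covariate is named, the choice could be made after unblinding.

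**Working it through.** **Inputs from the documents.** Response rates: "If we assume that 45% of the subjects in the active treatment arm will have successful pain relief versus 25% in the sham arm" (Protocol 11.3). Target: "with 80% power at a 5% level of significance using the POWER procedure in SAS v9.4". Sidedness: "All statistical tests will be two-sided" (Protocol 11.7.1). Planned size: "180 evaluable subjects are required, 90 per group". Achieved size: 109 (SAP Introduction), taken as 55 versus 54.

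**Assumptions.** The documents give neither the share of mild first attacks nor response by baseline pain. I take a mild share of 30–50% and a sham-arm gap between moderate/severe and mild attacks of 0 to 30 points. Overall rates are held at 45% and 25%, with one odds ratio across strata. Example with 50% mild and a 20-point gap: sham 15% (mild) and 35% (moderate/severe), active 31.6% and 58.4%, odds ratio 2.61. Check: 0.5×31.6 + 0.5×58.4 = 45.0.

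The gap has a ceiling. Sham response in mild attacks is 25 − (1 − mild share)×gap. With 30% mild, a 30-point gap gives 25 − 0.7×30 = 4%, and a 40-point gap gives 25 − 0.7×40 = −3%, which is impossible. I stop at 30.

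**Step 1: the plan's own figure.** With pooled variance and no continuity correction,

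n per group = [1.96·√(2·0.35·0.65) + 0.842·√(0.45·0.55 + 0.25·0.75)]² / 0.20² = 88.1, rounded up to 89.

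At 90 per group power is 80.8%, and 180/0.9 = 200. The planned size reproduces for the unadjusted test.

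**Step 2: power at the achieved size.** The same formula at 54.5 per group gives 59.3%.

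**Step 3: stratified test.** For stratum k with n_Ak active, n_Sk sham, t_k responders, a_k of them active, and N_k in total:
- E_k = n_Ak·t_k/N_k
- V_k = n_Ak·n_Sk·t_k·(N_k − t_k)/[N_k²(N_k − 1)]
- Z = Σ(a_k − E_k)/√ΣV_k

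Simulation at 55 versus 54, at least 60,000 trials per setting:

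| Sham gap (points) | Chi-squared power | Stratified power |
|---|---|---|
| 0 | about 60% | 59% |
| 10 | about 60% | 60% |
| 20 | about 60% | 62% |
| 30 | about 60% | about 66% |

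If mild attacks respond better instead, the stratified figures are 61–62% at 20 points and 64–66% at 30. At 55 per group, with mild shares from 20% to 50%, stratifying changed power by −1.5 to +5.9 points. At the planned 90 per group it changed power by −0.4 to +5.5 points. Type I error was near 5% for both tests.

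**Step 4: chance imbalance.** The SD of the between-arm difference in mild share is √[m(1−m)(1/55 + 1/54)]: 8.8 points at m = 0.3 and 9.6 at m = 0.5. With a 30-point gap, one SD moves the treatment difference by about 0.30×8.8 = 2.6 to 0.30×9.6 = 2.9 points. The standard error of that difference is √(0.45·0.55/55 + 0.25·0.75/54) = 8.9 points.

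**Step 5: the single trial.** The arms differ by at least 10 points in mild share in 25–32% of simulated trials. With a 20-point gap, chi-squared power in those trials is 44–45% when the active arm has the excess and 74–75% when sham has it. The stratified test stays at 60–62% either way. With a 30-point gap the swing is about 35% to 82%, against 65–66%. The two tests disagree on significance in about 8% of all trials at 20 points and 13% at 30.

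**The case against.** The strongest reply is that nothing is broken. The planned test holds its level, the sample size is right for it, and chance imbalance is already in its standard error. A shift of about 3 points per SD against a standard error of 8.9 is ordinary sampling variation. All of this stands, and it is why the point is an improvement only.

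The gain is also conditional. At gaps of 0–10 points it is nil or slightly negative, and the 30-point figures need very low sham response in mild attacks (4–10%). A harder hurdle on paper need not mean lower response. This stands too, although a gap in the opposite direction gives similar gains.

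Mild versus moderate/severe is an imperfect stratum: severe must fall two grades, while moderate and mild must each fall one. That is fair, and three levels would follow the definition more closely if counts allow.

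The plan is not silent. It permits logistic adjustment and tests 2-hour pain freedom, which has one target for every baseline level, as a secondary endpoint. It also analyses moderate/severe attacks separately. None of these commits to adjusting the primary comparison, and the last drops mild attacks and so answers a different question.

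The public SAP is abridged and ends at analysis sets. A reader might infer that the full SAP contains no adjustment. The public text cannot show that; it shows only that no commitment is visible.

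**Conclusion.** The point holds as a refinement. The response hurdle varies with baseline pain, baseline pain is collected before treatment, and the visible plan does not commit to using it in the primary comparison. At 109 subjects, stratifying takes power from about 60% to 59–60% at a gap of 0–10 points, 62% at 20 and about 66% at 30. It also makes the result of the one trial much less dependent on how mild attacks happened to fall between arms. These figures rest on 45% versus 25% overall, an assumed 30–50% mild share, an assumed gap and a common odds ratio.

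A reader might go further and infer that the unadjusted test is biased or inflates type I error, or that power is certainly being lost. The documents do not support either. Type I error is about 5% over repeated randomizations, and whether power is lost turns on a gap that the documents do not give. Nor does the point call for a different endpoint.

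**What to change.** While the data are still blinded, prespecify in the SAP:
- as the primary comparison, a Cochran-Mantel-Haenszel test stratified by baseline pain of the first eligible attack (mild versus moderate/severe, or three levels if cell counts allow), with a stratified risk difference and 95% CI;
- the unstratified chi-squared and Fisher's exact tests as sensitivity analyses;
- a table of baseline pain by arm, because it is measured after randomization and self-practice, though before treatment.

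If the sponsor prefers not to change the primary test this late, the least useful step is to name the stratified analysis as a committed sensitivity analysis.

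No new data are needed. The costs are up to about 1.5 points of power if baseline pain does not predict response, and a late, though blinded, change of primary test that must be dated and justified.
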